5. INVESTIGATIONAL PLAN

5.1. Study Design

This will be an open-label, randomised, 2-treatment period, single-dose crossover Phase I study conducted in healthy smokers as shown below:

Figure 1: Study Design Overview

The study will be comprised of a pre-study screen, followed by 2 treatment periods (1 and 2) and a post-study follow-up.

Screening (Day -28 to Day -1): Screening assessments will be carried out within 28 days before first administration of cytisine.

Baseline (Day 0): Baseline assessments will be carried out one day before the first administration of cytisine.

Treatment Periods (Day 1 to Day 5): Eligible subjects will receive a single-dose of cytisine under fed and fasted conditions during the 2 treatment periods.

- Each treatment period will be approximately 2 days' duration in which plasma and urine samples will be collected for 48 hrs.
- Subjects will arrive at the Clinical Unit on Day 0 and will undergo an overnight fast of at least 10 h prior to dosing on Day 1. Randomisation will occur on the morning of Day 1, Period 1, at least 1 hour prior to first dosing.
- Cytisine will be administered under fasted (after an overnight fast of at least 10 h) or fed (after a high fat breakfast) conditions with the last plasma and urine sample occurring at 48 h postdose (before the second cytisine dosing on Day 3). All subjects will stay overnight on Day 2 and undergo an overnight fast of at least 10 h prior to dosing on Day 3.
- Pharmacokinetic (PK) samples (plasma and urine) will be collected predose and up to 48 h postdose during each period for the measurement of plasma and urine cytisine concentrations. Safety will also be evaluated at specified times.
- Final ECGs and blood draw for repeat haematology and chemistries will be obtained just prior to discharge on Day 5.
- There will be at least 48 hours between dose administrations on Day 1 and Day 3.

Post Study: Post study telephone follow-up will be conducted 6 to 8 days after the last dose of cytisine. If any adverse events are recorded at post study telephone assessment, arrangements

will be made with the subject, so that they are followed-up appropriately and the final outcome determined.

The end of study is defined as completion of safety follow-up on all subjects. The maximum duration of this study is estimated to be around 6 weeks (screening to last subject's last visit, via telephone contact).

5.2. Discussion of Study Design

This study design minimizes the influence of inter-subject variability, which is assumed to be higher than the intra-subject variability, as each subject will be administered cytisine in both the fed and fasted states. As each subject serves as his own control, the precision of the comparison should be improved.

The blood and urine samples for the determination of cytisine plasma and urine concentrations will be collected up to 48 hours after cytisine administration. Taking into account the known terminal elimination half-life of cytisine (about 4 hours), this sampling schedule is expected to provide a reliable estimate of the extent of exposure.

The washout of at least 48 hours between dose administration will allow a complete elimination of cytisine between doses and is deemed sufficiently long to avoid any relevant carry-over effect.

6. SELECTION OF STUDY POPULATION

Approximately 12 subjects represented in the Urine/PK Analysis Set will be required to complete the study.

The study is to be conducted in healthy subjects who are current smokers. A healthy subject population with carefully considered inclusion/exclusion criteria will avoid the potential for interaction of cytisine with any underlying disease state or concomitant medication that might be necessary to administer to patients, while ensuring that subjects are fit and well enough for participation in the study. Since smokers are the intended population for cytisine treatment, current smokers will be enrolled in the study.

The following eligibility criteria are designed to select subjects for whom protocol treatment and procedures are considered appropriate. All relevant medical and non-medical conditions should be taken into consideration when deciding whether this protocol is suitable for a particular subject.

6.1. Inclusion Criteria

6.1.1. To be Confirmed at Screening

1. Subject is current cigarette smoker.
2. Healthy males and females between 18 and 55 years of age.
 - a. If a female subject of child bearing potential, a negative pregnancy test at screening and admission and willing to use an effective method of contraception (unless of non-childbearing potential or where abstaining from sexual intercourse is in line with the

- preferred and usual lifestyle of the subject) from first dose until 3 months after last dose of cytisine.
- b. If a female subject of non-child bearing potential, a negative pregnancy test at screening and admission. For the purposes of this study, this is defined as the subject being amenorrheic for at least 12 consecutive months or at least 4 months post-surgical sterilisation (including bilateral fallopian tube ligation or bilateral oophorectomy with or without hysterectomy). Menopausal status will be confirmed by demonstrating at screening that levels of follicle stimulating hormone (FSH) fall within the respective pathology reference range. In the event a subject's menopause status has been clearly established (for example, the subject indicates she has been amenorrheic for 10 years), but FSH levels are not consistent with a post-menopausal condition, determination of subject eligibility will be at Investigator's discretion following consultation with the Sponsor.
 - c. If a male subject, willing to use an effective method of contraception (unless anatomically sterile or where abstaining from sexual intercourse is in line with the preferred and usual lifestyle of the subject) from first dose until 3 months after last dose of cytisine.
3. Subject with a body mass index (BMI) of 23-28 kg/m². BMI = body weight in kg / [height in m²].
 4. Subject with no clinically significant abnormal serum biochemistry or haematology values within 28 days before the first dose of cytisine.
 5. Subject with negative urinary drugs of abuse screen, determined within 28 days before the first dose of cytisine (a positive result may be repeated at Investigator's discretion).
 6. Subject with negative human immunodeficiency virus (HIV), hepatitis B surface antigen (Hep B) and hepatitis C virus antibody (Hep C) results.
 7. Subject with no clinically significant abnormalities in 12-lead ECG determined after minimum of 5 minutes in supine position within 28 days before the first dose of cytisine.
 8. Subject with no clinically significant abnormalities in vital signs (systolic blood pressure between 90-140 mmHg, diastolic blood pressure (DBP) between 50 and 90 mmHg, and pulse rate (PR) between 40-100 bpm, measured on the dominant arm after minimum of 5 minutes in supine position) determined within 28 days before first dose of cytisine.
 9. Subject must be available to complete the study (including post study follow-up) and comply with study restrictions.
 10. Subject must provide written informed consent to participate in the study.

6.1.2. To be Re-Confirmed Prior to Dosing

1. Subject continues to meet all screening inclusion criteria (before the cytisine dose).
2. Subject has a negative urinary drugs of abuse screen (including alcohol).
3. Female subject has a negative urine pregnancy test.

6.2. Exclusion Criteria

6.2.1. To be Confirmed at Screening

1. Known hypersensitivity/allergy reaction to varenicline, other cytisine-derivatives or any of the excipients in the [REDACTED] formulation [REDACTED]).
2. History of severe hypersensitivity reactions to any other drugs.
3. History of any medical condition (e.g. gastrointestinal, renal or hepatic) or surgical condition (e.g. cholecystectomy, gastrectomy) that may affect drug pharmacokinetics (absorption, distribution, metabolism or excretion).
4. Female subjects who are breast feeding.
5. Difficulty in donating blood on either arm or known history.
6. History of alcoholism or drug abuse within last 2 years.
7. Use of prescription or non-prescription drugs, including vitamins, herbal and dietary supplements within 14 days (or 5 half-lives, whichever is longer) prior to the cytisine dose, unless in the opinion of the Investigator the medication will not interfere with the study procedures or compromise subject safety.
8. Participated in any investigational drug clinical trial within the previous 3 months or a marketed drug trial within the previous 30 days prior to randomization on Day 1 of Period 1.
9. Donation of 450 mL or more blood or had history of significant blood loss due to any reason or had plasmapheresis within 3 months before the cytisine dose.
10. Any inability or difficulty in fasting.
11. Inability to communicate well with Investigators (i.e., language problem, poor mental development or impaired cerebral function).
12. Any other condition that the Principal Investigator considers making the subject unsuitable for this study.

6.2.2. To be Re-Confirmed Prior to Dosing:

1. Development of any exclusion criteria since screening.
2. Use of prescription or non-prescription drugs, including vitamins, herbal and dietary supplements since screening, unless in the opinion of the Investigator the medication will not interfere with the study procedures or compromise subject safety.
3. Participation in a clinical study since the screening visit.
4. Donation of 450 mL or more blood since the screening visit.

6.3. Removal of Subjects from Therapy or Assessment

Each subject will be informed of their right to withdraw from the study at any time and for any reason.

An Investigator will withdraw a subject from the study at any time for any of the following reasons:

- If a subject experiences a serious or intolerable AE, that prevents them from continuing.
- If a subject incurs a significant protocol violation which impacts on their safety or the scientific integrity of the study (this will be discussed on a case-by-case basis with the Sponsor).
- At the request of the Sponsor.
- If it is considered that the subject's health is compromised by remaining in the study or the subject is not sufficiently cooperative.
- If a subject is lost to follow-up.

The reasons for any subject withdrawal will be recorded on the study completion form of the case report form (CRF).

If a subject is withdrawn or chooses to withdraw from the study for any reason, every possible effort will be made to perform the evaluations described for the post-study follow-up. The data collected from withdrawn subjects will be included in the study report.

In the event of any abnormalities considered to be clinically significant, subjects will be followed up with appropriate medical management until values are considered to be clinically acceptable. Referral or collaborative care will be organised if considered necessary.

Since approximately 12 subjects are to be included in the urine excretion/PK dataset to complete the study, subjects who withdraw from the study before receiving any study medication will be replaced. Subjects who are withdrawn from the study due to significant drug-related AEs will not be replaced. Replacement of all other subjects withdrawn from the study after receiving study medication will be decided on a case-by-case basis by the Principle Investigator (or delegate) and Sponsor.

7. RESTRICTIONS PRIOR AND DURING THE STUDY

To avoid possible negative effects on the measurement of plasma drug concentrations and/or on subject's safety, several restrictions are to be adopted as outlined in the eligibility criteria and in the following sections.

7.1. Confinement

Each subject will complete 2 treatment periods (Period 1 and Period 2) in confinement. This period will require 5 nights stay (arrive at the unit in the afternoon of Day 0 and discharged 48 hours post second cytosine dose on Day 5).

7.2. Diet and Fluid Restrictions

7.2.1. Meal Times

Fasting:

- Subjects will fast overnight for at least 10 hours before dosing.
- Lunch will be served: approximately 4 h post-dose.
- Dinner will be served: approximately 8 h post-dose.
- Snack will be served: approximately 12 h post-dose.

Fed:

- Subjects will fast overnight for at least 10 hours.
- A high fat breakfast will be served at 30 min pre-dose (breakfast needs to be finished at least 5 minutes before dosing).
- Lunch will be served: approximately 4 h post-dose.
- Dinner will be served: approximately 8 h post-dose.
- Snack will be served: approximately 12 h post-dose.

The example of a high fat (approximately 50% of total caloric content of the meal) and high-calorie (approximately 800-1000 calories) breakfast provided in the US Food and Drug Administration guidance document for food-effect bioavailability and fed bioequivalence studies (Guidance for Industry, U.S. Department of Health and Human Services Food and Drug Administration Center for Drug Evaluation and Research (CDER), December 2002) is approximately 150, 250 and 500-600 calories from protein, carbohydrate and fat respectively. Suggested content to be: 2 eggs fried in butter, 2 strips of bacon, 2 slices of toast, 4 ounces of hash brown potatoes and 8 ounces of whole milk. Consumption of the standardized breakfast will be documented.

7.2.2. Fluid Intake

No fluids (apart from water taken with dose) are allowed from 1 h prior to dosing until 1 h afterwards. Water is then allowed ad libitum. Decaffeinated tea and coffee as well as squash/cordial are allowed from 4 h post-dose.

7.2.3. Smoking

There will be minimal restrictions to smoking during days of confinement, such as all smoking must occur within designated area(s) only and subjects cannot smoke during active PK sampling period (i.e. subjects must have their last cigarette a minimum of 2 hours before dosing and can only start smoking after final PK sample). Subjects will go for a cigarette as a group and will need to have their last cigarette before 23:00 while they stay in the clinic. Clinic staff will review these guidelines with subjects during confinement and will monitor compliance.

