8.8. Selection and Timing of Dose for Each Subject

Doses will be administered at approximately 9:00 a.m. All subjects will be fasting for at least 10 h overnight prior to dosing in both treatment periods. Subjects assigned to be fasting prior to dosing will remain fasting until lunch and subjects assigned to be fed prior to dosing will start their high-fat breakfast 30 minutes prior to the dose. Lunch will be provided 4 h after dosing for all subjects.

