12.2. Pharmacokinetic Urine Collection

Eleven urine samples will be collected at the following time points during each period:

Table 7: Urine Sampling for Pharmacokinetic Assessments During each Period

Urine Sample Number	Time from Dosing
1	Pre-dose (Pre-dose urine samples will be collected within 30 minutes prior to dosing)
2	00:00-02:00*
3	02:00-04:00
4	04:00-08:00
5	08:00-12:00
6	12:00-24:00
7	24:00-26:00
8	26:00-28:00
9	28:00-32:00
10	32:00-36:00
11	36:00-48:00

*Each urine collection must contain all urine excreted within the timeframes as indicated.

The urine collection containers will be identified with a bar coded label bearing details of the study number, subject number, study period number, sampling time-point, sample type and a unique 9 digit identification number.

The urine collection containers will be kept chilled (at approximately 4°C) during collections. After the termination of each fractional collection the volume excreted will be recorded and 2 x 10 mL aliquots retained for determination of cytisine concentrations. The aliquots will be labelled identically to the original collection container and will be stored at -20°C pending analysis.

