### 6.2 PK SET

The PK Set will include all subjects who receive both doses of cytosine and have sufficient plasma concentration-time profiles complying with the following criteria:

- Do not have an occurrence of vomiting or diarrhoea which renders the concentration profile unreliable (e.g. if vomiting occurs at or before 2 times median  $T_{max}$ );
- Do not use a concomitant medication which renders the concentration profile unreliable;
- Do not have a pre-dose concentration that is greater than 5% of the corresponding  $C_{max}$ ;

- Have at least one evaluable concentration that is preceded by a lower evaluable concentration and followed by a lower evaluable concentration for the calculation of  $C_{max}$ ,  $T_{max}$  and AUCs (i.e. at least 3 evaluable concentrations in total);
- Do not violate the protocol (major protocol deviation) in a way that may invalidate or bias the results.

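### Does the smoking rule in Protocol 7.2.3, which read literally leaves no smoking window for about 98 hours, need to be changed?

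*Protocol*

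**What the plan says.** Protocol 7.2.3 makes three statements about smoking in the unit:

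- It opens with "There will be minimal restrictions to smoking during days of confinement".
- It then bars smoking while PK sampling is active and explains this as meaning that "subjects must have their last cigarette a minimum of 2 hours before dosing and can only start smoking after final PK sample".
- It adds that "Subjects will go for a cigarette as a group and will need to have their last cigarette before 23:00 while they stay in the clinic", and that staff will go over the guidelines with subjects and check compliance.

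The timetable is set elsewhere. Protocol 7.1 has subjects "arrive at the unit in the afternoon of Day 0" and stay five nights, until 48 h after the second dose. Protocol 8.8 states "Doses will be administered at approximately 9:00 a.m", and Protocol 11 puts the doses on Day 1 and Day 3. Protocol 5.1 describes Period 1 "with the last plasma and urine sample occurring at 48 h postdose (before the second cytisine dosing on Day 3". Table 6 places the last plasma draw at 48 h. Table 7 runs urine collection to 48 h without a gap, with the note "Each urine collection must contain all urine excreted within the timeframes as indicated".

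On the analysis side, SAP 5 requires every deviation to be classed as major or minor before database lock. SAP 6.2 makes it a condition of the PK Set that subjects "Do not violate the protocol (major protocol deviation) in a way that may invalidate or bias the results", and SAP 6.3 applies the same condition to the Urine Excretion Set. SAP 11.7.2 lists tobacco use and cigarette collection.

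**The concern.** The explanatory clause in 7.2.3 ends the ban at the final PK sample. In this schedule that sample falls at 48 h, just before the next dose, while the ban for that next dose has already started 2 h earlier. No smoking window is left between doses. The group breaks and the 23:00 limit could then apply in practice only on the evening of Day 0, which is hard to square with an opening sentence promising few restrictions.

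If the wording is unsettled, a cigarette on Day 2 or Day 4 is either permitted or a breach. That could matter in two ways. A breach has to be graded, and a major deviation that may bias the results removes a subject from an analysis set of only 12. And smokers kept abstinent for about four days may report abstinence symptoms, which SAP 11.6.1 would tabulate as treatment-emergent under whichever condition was given in that period.

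**Working it through.** **Inputs.** Dosing at about 09:00 (Protocol 8.8) on Days 1 and 3 (Protocol 11). Ban from 2 h before the dose to the final PK sample (7.2.3). Final sample at 48 h (5.1, Tables 6 and 7). Evening limit 23:00 (7.2.3). Half-lives 4.59 h fasted and 4.77 h fed (Table 3, non-smokers, original formulation) and 4.8 h (Table 2, smokers).

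**Dose interval.** 09:00 on Day 1 to 09:00 on Day 3 = 48 h, which matches the interval in Protocol 5.1.

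**Literal reading.**
- Period 1: 07:00 Day 1 to 09:00 Day 3 = 2 + 48 = 50 h.
- Period 2: 07:00 Day 3 to 09:00 Day 5 = 50 h.
- Overlap on Day 3, 07:00 to 09:00 = 2 h.
- Total: 50 + 50 − 2 = 98 h, with no gap. A window would open only if the second dose came more than 50 h after the first.

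**Looser reading, ban ending at the 24 h plasma sample.**
- Ban per dose: 2 + 24 = 26 h, ending at about 09:00 on Day 2 and Day 4.
- Time to the 23:00 limit: 14 h on each day, 28 h in total.
- In post-dose time the window is 24 to 38 h.

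**Looser reading, ban ending at the 16 h plasma sample.** The ban ends at 09:00 + 16 h = 01:00, which is already past 23:00, so smoking again resumes on Day 2 or Day 4, though possibly before the 24 h draw.

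**What the disputed cigarettes could touch.**
- *Plasma.* Of the 17 post-dose draws, 15 are at or before 16 h; the other two are at 24 h and 48 h. No draw is scheduled between 24 and 38 h. Terminal-phase fraction remaining at 24 h is 2^(−24/t½): 2^(−24/4.59) = 2.7%, 2^(−24/4.77) = 3.1%, 2^(−24/4.8) = 3.1%. At 16 h the same formula gives about 9% to 10%. Cmax and Tmax are expected well before either time: Table 3 gives Tmax of 0.75 h fasted and 2.75 h fed.
- *Urine.* A window of 24 to 38 h overlaps 5 of the 10 post-dose intervals (24–26, 26–28, 28–32, 32–36, 36–48 h). These are late intervals: Protocol 2.2 reports about 82% of the dose recovered within 24 h in the earlier fasted study.
- *Mechanism.* Neither document states that smoking alters the absorption, clearance or excretion of cytisine.
- *Fed/fasted contrast.* The ban is identical in both conditions. Six subjects take each order, and the ANOVA in SAP 11.4.2.1 and 11.4.4.1 has terms for period, sequence and subject within sequence.
- *Adverse events.* Under all three readings subjects abstain from about 07:00 on each dosing day until at least 01:00 the next morning. Abstinence symptoms can therefore enter the post-dose tables whichever reading is used. The literal reading lengthens the exposure, but the two orders are balanced. Causality is graded separately (Protocol 13.2.4).

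**The case for a change.** The strongest case for a change is that the text gives opposite answers to a simple question. Protocol 5.1 counts both plasma and urine as PK samples and puts the last of each at 48 h, so the literal reading is not forced. The looser reading has at least two possible end points, and neither is written down. Staff are asked to monitor compliance with a window they must infer. The SAP's listings record who smoked, but not whether it was allowed. With 12 subjects, each exclusion costs 1/12, or 8.3%, of an analysis set. The repair would be a sentence or two.

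The textual part of this stands: the sentences of 7.2.3 do not agree with each other or with the 48 h schedule, and the sponsor and investigator have to read them together.

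The consequences do not follow. Exclusion requires more than a breach: it must be a major deviation that may invalidate or bias the results, and the documents give no reason to expect that of a cigarette a day or more after dosing. Grading passes through the data review meeting before lock (SAP 5 and 9.3) and is confirmed by the sponsor (SAP 11.7.2), so it is not left to one person's reading of 7.2.3. The urine argument is also less firm than it looks, since Protocol 11 names the last PK sample and the last urine sample as separate things. And because smoking is by staff-led group break at one site, different subjects are unlikely to be held to different windows.

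**Conclusion.** The 98 h figure is correct on a literal reading, and the wording is loose. It is a missing detail in a conduct rule that the unit will fill when it schedules its smoking breaks; which window applies is for the sponsor and investigator and is not judged here. The difference between the literal reading and the 24 h reading is 28 h of permitted smoking per subject, at 24 to 38 h after a dose. No endpoint, analysis set, model or sample-size figure depends on which reading is used, and the fed/fasted comparison, urinary recovery and safety summaries would be equally interpretable under any of them.

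This rests on four assumptions: dosing close to 09:00 on both days; half-lives in this study near the 4.59 to 4.8 h the protocol quotes; no effect of smoking on cytisine kinetics, for which the documents offer no evidence either way; and one window applied to all subjects in both periods. If different windows had been applied to different subjects or periods, that would show in the tobacco and cigarette listings and could be taken up at the data review meeting.
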